Official Title: The Value of Home Chlorhexidine Pre-Surgical Wash before Spine Surgery

NCT Number: NCT02767427

PI: [name] [name]

Site: Columbia University Irving Medical Center

Version: 07/02/2018

Study Purpose and Rationale:

Surgical site infections lead to significant morbidity and mortality. These complications lead to severe clinical, and economic, burdens across surgical disciplines, and may have especially harmful consequences in spine surgery, where they can lead to extensive revision surgeries as well as neurologic sequelae, or even death.

Other trials have examined the effects of presurgical cleansing with chlorhexidine with mixed results. For example, Murray et al. performed a prospective, randomized study examining the effect of CHG cloth treatment at home preoperatively (1). Their study, which was industry sponsored, concluded that pre-cleansing led to decreased bacterial culture positivity preoperatively. However, they reported only on the results of their sample taken in the preoperative holding area. The most relevant data is arguably the bacterial burden after preoperative prep, to determine whether the level equalizes in both groups after the chlorhexidine is applied immediately preoperatively. Additionally, they looked at its use before shoulder surgery, while we are looking at the effects prior to spine surgery.

Another study by Ng et al. prospectively studied the effect of chlorhexidine foot washes on patients prior to foot and ankle surgery and found reductions in bacterial burden after washing (2). They analyzed bacterial flora qualitatively rather than quantitatively, reporting only culture positivity rather than bacterial colony counts. They claim that CHG decreased flora intraoperatively, however their "intraoperative" sample took place after washing and before prep and drape; it could more precisely be labeled a preoperative sample. It was taken about twenty minutes after washing, so it is not surprising that the burden was decreased in this actually preoperative sample. There was a reduction postoperatively in the chlorhexidine footbath group. However, this was not statistically significant.

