Significant effort has been put forth by surgeons in the past few decades to decrease the rate of surgical site infections. One intervention has been the adoption of chlorhexidine use by the patient at home preoperatively. There has been conflicting evidence about its potential efficacy in decreasing bacterial loads and infection rates across surgical populations. This intervention has been a subject of numerous trials and reviews over the last several years and has recently been a topic of interest in the orthopedic surgery literature as well. However, no prior study has analyzed the benefit of such an intervention with regards to the field of spine surgery.

Scientific Abstract:

To our knowledge no prior study has evaluated the effects of preoperative skin cleansing on the cutaneous bacterial burden for patients undergoing spine surgery. Surgeons use various methods to decrease the risk of infection in patients perioperatively. We would like to conclusively determine whether or not at-home preoperative skin cleansing with chlorhexidine decreases the bacterial burden pre-operatively for patients undergoing spine surgery, and if these effects are eliminated after the pre-surgical chlorhexidine prep. We will perform a prospective, randomized clinical trial to assess the impact of home chlorhexidine wipes and evaluate whether this intervention leads to a change in bacterial counts on patients pre- and intra-operatively. Validating their efficacy will allow optimal protocols to be

designed that contribute to improved outcomes without adding undue mental or financial burden on patients.

Lay Abstract:

To our knowledge no prior study has evaluated the effects of cleaning the skin at home before surgery in patients undergoing spine surgery. We will perform a clinical trial to see if patients who use the chlorhexidine cleansing wipe have decreased amounts of bacteria on their skin when they arrive for their scheduled spine surgery. Spine surgeons strive to decrease infections in their patients, so it is important to see if this intervention helps to do this.

Research Question/Hypothesis:

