We plan to assess the effect of preoperative chlorhexidine skin cleansing on cutaneous bacterial loads.

1. We hypothesize that preoperative washing will decrease overall bacterial burden upon patient arrival to the pre-operative holding area and before the pre-surgical prep.
2. We also believe that the immediate pre-operative and the intra-operative bacterial counts will be unaffected by this intervention.

Study Design:

We will perform a prospective, randomized clinical trial at Columbia University, specifically the Allen Pavilion as our test site.

Clinical Trial:

We will prospectively analyze 40 patients undergoing spine procedures at Columbia University. After attaining IRB approval, and confirming that all surgeons included in this study will abide by the standardized preoperative protocol, we will begin trial enrollment.

Patients undergoing spine surgery will be included after informed consent with the surgical team during their preoperative clinical evaluation. Randomization will occur through use of numbered envelopes with cards inside with detailed instructions for patients in the chlorhexidine versus placebo groups; grouping will be determined by a random number generator matching to the envelope numbers. The attending surgeon, as well as the microbiology lab analyzing the sample, will be blinded to the selected intervention.

Inclusion Criteria:

- 18 years old or older
- Scheduled for elective spine surgery at Columbia University Medical Center

Exclusion Criteria:

- Unable to apply at-home chlorhexidine wipe by themselves
- Deemed "high risk" preoperatively by the treating surgeon
- Diagnosed with spine trauma
- Undergoing deformity correction surgery
- Unable to consent to the terms of the surgery
- Known infection at time of the index procedure
- Hospitalized within 1 week pre-operatively
- Allergic to chlorhexidine
- Immunocompromised
- End stage renal disease on dialysis

- Local or systemic skin disease (such as psoriasis, eczema, etc.)
- Open skin wounds

Patient Criteria

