Patients will be randomized to the chlorhexidine or no additional intervention groups. Patients will be randomized to use 4% chlorhexidine cloths, while the other half receive no additional intervention. Those randomized into the CHG home-application group will be asked to shower the night before surgery, and to use a standardized pre-packaged chlorhexidine gluconate wipe (that they would receive at their pre-surgical consultation) on their surgical site after thoroughly drying those areas. They will be asked to use a second wipe in each area the morning of surgery. Those who forget to use the wipe in the morning are allowed to use the wipe in the pre-operative area and included if this occurs more than one hour before skin prep. The surgical sites will be analyzed in two groups: anterior cervical and posterior spine. Each of these two groups will be randomized separately. All patients will undergo a standardized preoperative cleansing regimen. Once positioned, they will be cleansed with an alcohol solution. Then, the surgical site (either the anterior portion of the neck or the posterior area of the spine) will be scrubbed with chlorhexidine-soaked brushes and then painted with chlorhexidine solution. Perioperative antibiotics will be given per attending surgeon preference.

Specimen Sampling

Cutaneous samples will be taken from the surgical site of each patient at each time point. Initial skin sample would be taken in the office at the preoperative clinical visit at time of booking. The next specimen will be acquired pre-operatively after the patient is positioned on the operating table, before the skin prep. A third sampling occurs immediately before draping, after the skin prep had been given adequate time to completely dry. The fourth sample will be taken 1hr after the start of the case from superficial subcutaneous tissue. All specimens were taken by a sterile BD E-Swab, which will be rubbed 10 times (five times in one direction, five times in the other) lightly along a 5cm site the surface of the site being used for the incision. This swab will be then placed in the ESwab collection system. All samples will be sent immediately after acquisition to the microbiology lab for analysis within twenty-four hours.

Statistical Procedures:

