Data will be analyzed in intent-to-treat manner. All patients will be asked in the preoperative holding area about their compliance to the home cleansing regimen. Those who are noncompliant or only partially compliant with their treatment will still be included in the intent-to-treat analysis and will also be removed for subsequent analysis of only patients who were fully compliant with treatment. Power analysis will be performed before the start of the trial in order to achieve adequate power to detect significant decreases in the bacterial burden after intervention. The standard deviation of the data will be assessed after the pilot trial so that this calculation can be performed. Data analysis will be done through multivariate analysis with logistic regression and chi squared analysis, using SPSS.

Recruitment:

Patients will be enrolled prospectively as they present to the medical practice of the spine practice. If they are eligible based on inclusion criteria and exclusion criteria, they will be offered informed consent and enrollment into the trial. Only patients who present to the offices of the spine attendings included in the study and who are eligible will be identified and the study discussed with them. Pilot trial patients will be recruited from word-of-mouth discussion with study investigators and healthcare staff within Columbia.

Potential Benefits:

Patients undergoing adult spine surgery at CUMC do not currently receive at-home chlorhexidine wipes. They are an additional anti-microbial measure that possibly decrease the amount of bacteria on the skin. Through this trial, half of the enrollees will obtain this additional potentially anti-microbial step in their preoperative regimen, which could potentially decrease their risk of developing surgical site infections.

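### Hypothesis 1 is about bacterial counts and power rests on a standard deviation, but the only analyses named are for categorical outcomes and none estimates the difference in counts

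*Combined protocol and SAP*

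**What the plan says.** The Scientific Abstract says the trial will "evaluate whether this intervention leads to a change in bacterial counts on patients pre- and intra-operatively". Hypothesis 1, under Research Question/Hypothesis, is that "preoperative washing will decrease overall bacterial burden upon patient arrival to the pre-operative holding area and before the pre-surgical prep". Study Purpose and Rationale faults an earlier foot and ankle study: "They analyzed bacterial flora qualitatively rather than quantitatively, reporting only culture positivity rather than bacterial colony counts".

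Statistical Procedures seeks "adequate power to detect significant decreases in the bacterial burden after intervention" and adds: "The standard deviation of the data will be assessed after the pilot trial so that this calculation can be performed". The analysis itself is one sentence: "Data analysis will be done through multivariate analysis with logistic regression and chi squared analysis, using SPSS". No section gives a cut-off, a growth grade, a transformation, a list of covariates or a primary time point for that analysis.

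Specimen Sampling includes a swab at the office visit, before the intervention, and a second on the operating table before skin prep. Statistical Procedures mentions neither. The Intervention section says "The surgical sites will be analyzed in two groups: anterior cervical and posterior spine" and "Each of these two groups will be randomized separately", without saying whether this means two separate analyses or one stratified analysis. Clinical Trial gives the total as 40 patients, and Intervention assigns half to each arm.

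**The concern.** A standard deviation is the natural input for comparing means. Logistic regression and chi-squared work on categories. If the trial is sized from the pilot SD and hypothesis 1 is then tested on categories, the sample size was calculated for a different test and may be too small for the one used. Neither named method yields the size of the fall in counts, which is the aim. Because the coding of the outcome is open, it could also be chosen after the data are seen. With about 20 patients per arm there is little precision to spare.

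The point concerns the pre-prep sample, where hypothesis 1 is tested. After skin prep and in subcutaneous tissue most swabs may be negative, and a categorical analysis could suit those samples.

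**Working it through.** **1. The plan's own figure.** The total of 40 cannot be reproduced: no alpha, power, effect size or SD is stated. Everything below is illustrative and assumes two-sided alpha 0.05. Halving 40 gives 20 per arm.

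**2. Continuous outcome, no zeros.** Detectable difference at 80% power = (1.960 + 0.842) × √(2/20) = 0.886 SD.

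**3. The same effect cut into positive/negative.** If a share q of controls is positive, the cut lies c = Φ⁻¹(1−q) SDs from the control mean, and treated positivity is 1 − Φ(c + 0.886).
- q = 50%: c = 0, treated 18.8%
- q = 80%: c = −0.842, treated 48.2%
- q = 90%: c = −1.282, treated 65.4%

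Power at n = 20 per arm is Φ{[(p₁−p₂)√n − 1.960√(2p̄(1−p̄))] / √(p₁(1−p₁)+p₂(1−p₂))}, which gives 55%, 56% and 46%. Reaching 80% takes 36, 35 and 44 per arm instead of 20.

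**4. With a detection limit.** Step 3 favours the t-test, because negative swabs also distort log counts. So assume within-region SD 1 log10, fall 1 log10, regions 0.5 log10 apart with 10 per arm in each, and values below 1 log10 set to zero. With control mean m, control positivity is ½[Φ(m−1.25) + Φ(m−0.75)]; for the treated arm replace m by m−1. Power at 20 per arm, regions pooled, comes from simulation (2,500 trials per scenario, so roughly ±2 points):

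| Control positive | Treated positive | Chi-squared on positive/negative | t-test on log counts |
|---|---|---|---|
| 31% | 7% | about 50% | 51–53% |
| 50% | 17% | 65% | 68% |
| 69% | 31% | 64% | 77% |
| 83% | 50% | 64% | 81% |
| 97% | 83% | 28% | 84% |

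At 31% the near-tie flatters chi-squared somewhat: 77–78% of those trials have an expected cell below 5, and Fisher's exact test has 36–38% power.

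**5. Sample size for 80% power on the same basis.** Chi-squared: n = [1.960√(2p̄(1−p̄)) + 0.842√(p₁(1−p₁)+p₂(1−p₂))]² / (p₁−p₂)².
- 69% row: m = 1.5, p₁ = ½(0.599+0.773) = 0.686, p₂ = 0.314. n = (1.386 + 0.552)² / 0.372² = 27.1, so 28. The t-test with zeros kept needs about 22.
- 50% row: m = 1, p₁ = 0.500, p₂ = ½(0.106+0.227) = 0.166. n = 30.1, so 31. The t-test with zeros kept needs about 26.

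**6. Office swab.** Ignoring zeros, adjusting for a baseline with correlation ρ reduces the SD to SD × √(1−ρ²). For the 0.886 SD effect, power rises from 80% to about 84%, 90% and 97% at ρ = 0.3, 0.5 and 0.7. The documents give no value of ρ.

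**7. Regions.** If the regions are analysed separately and split evenly (the split is not given), each has 10 per arm and the detectable difference becomes 2.802 × √(2/10) = 1.25 SD.

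**The case against.** The strongest reply is that logistic regression need not be binary. A cumulative-logit model on ordered counts is logistic regression, needs no cut-off and is closely related to a rank test, which in the step 4 model had about the same power as the t-test. Chi-squared might be meant for the categorical patient characteristics. This stands in part. A reader might infer that the plan dichotomises the counts, or cannot run without a cut-off; no section says so. But no ordinal model is specified, and one would neither match an SD-based power calculation nor estimate the difference in counts. The reference to multivariate analysis does not help, because the sentence ties it to logistic regression.

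Second, the wording about change and about decreases after intervention could imply comparison with the office swab. So a reader who infers that the swab has no role goes too far: its use is unspecified, not excluded.

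Third, the size rests on assumed inputs. That also stands, and at 31–50% control positivity the two tests nearly tie. A reader might instead set the textbook two-means size for a 1 SD fall, 16–17 per arm, against the chi-squared sizes. That is not like for like, because it ignores the zeros that a pilot SD would contain. The fair contrasts are those in step 5.

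**Conclusion.** The mismatch is established from the text alone: a count-based aim, SD-based power, and only categorical methods named, with no outcome coding and no stated use of the office swab. It should be fixed before the power calculation is done. It applies to hypothesis 1 and the pre-prep sample.

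Its cost in power is not established. Under the step 4 assumptions the loss runs from about 1–3 points when 31–50% of control swabs are positive, through 13 points at 69% and 17 at 83%, to 56 points at 97%. The documents give neither the positivity rate nor the SD. A reader might infer that the trial is shown to be underpowered, or that its analysis must lose most of its power; the documents support neither.

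**What to change.** For hypothesis 1, replace the analysis sentence with:

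*The primary analysis compares log10(count+1) at the pre-prep sample between arms by ANCOVA with treatment, log10(office-swab count+1) and region (anterior cervical / posterior), giving the difference with a 95% CI.*

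- Do the power calculation on the same log10 scale, with zeros handled the same way.
- Use one region-stratified rank test as the sensitivity analysis.
- Keep culture positivity as secondary, by chi-squared or exact test and logistic regression.
- State whether the two surgical regions are analysed separately. If so, fit the model within each region without the region term and base power on each region's size.

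**Cost.** The swabs are already planned, so no new samples are needed. The laboratory must report a quantitative count with its detection limit; Specimen Sampling says only that samples go for analysis. If the laboratory can only grade growth, use an ordinal logistic model on the grades, adjusted for the office swab and region, and size the trial for that model. The gain from the office swab depends on an unknown correlation. With many negative swabs the log10(count+1) difference understates the true fall: in the step 4 model a fall of 1.0 is estimated at about 0.65 when 50% of controls are positive. The report should therefore give the share of swabs below the limit in each arm.
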